For subjects randomized to the MK-8521 180 μg treatment group, Vial C will contain active MK-8521 and Vial D will contain placebo. The starting dose in the MK-8521 180 μg treatment group will be 60 μg (0.1 mL from each vial) from Visit 3/Day 1 through Day 6. The dose will then be escalated to 120 μg (0.2 mL from each vial) from Visit 4/Week 1 through Day 13, and to the final dose of 180 μg (0.3 mL from each vial) from Visit 5/Week 2 through Day 20. In order to maintain blinding with the MK-8521 300 μg treatment group (see above), the dose from Vial C will remain at 0.3 mL/day and the dose Vial D will increase to 0.5 mL/day from Visit 6/Week 3 for the remainder of the 12 weeks (approximately 63 days).

In order to maintain blinding with the MK-8521 treatment arms, subjects randomized to placebo will receive a dose escalation regimen consistent with that for MK-8521 300 μg and 180 μg treatment groups (see above). For subjects randomized to the Placebo treatment group, both Vial C and Vial D will contain placebo. The starting dose in the Placebo treatment group will be 0.1 mL from each vial from Visit 3/Day 1 through Day 6. The dose will then be escalated to 0.2 mL from each vial from Visit 4/Week 1 through Day 13, to 0.3 mL from each vial from Visit 5/Week 2 through Day 20, and to the final dose of 0.3 mL from Vial C and 0.5 mL from Vial D from Visit 6/Week 3 for the remainder of the 12 weeks (approximately 63 days).

Subjects who cannot tolerate 0.5 mL/day from Vial D may continue in the trial on 0.3 mL/day (180 µg/day for subjects randomized to active MK-8521) from each vial (refer to Section 5.2.1.2 for further details).

Protocol/Amendment No.: 004-02

Liraglutide Dosing

Subjects randomized to the liraglutide 1.8 mg treatment group will start at a dose of liraglutide 0.6 mg from Visit 3/Day 1 through Day 6, 1.2 mg from Visit 4/Week 1 through Day 13 and 1.8 mg from Visit 5/Week 2 for the remainder of the 12 weeks (approximately 70 days).

Subjects who cannot tolerate the 1.8 mg/day dose of liraglutide may continue in the trial on the 1.2 mg/day dose.

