The investigator may delay one step of the dose escalation by one week; however, the dose from each vial must reach 0.3 mL/day no later than Day 21.

Liraglutide Treatment Group

Subjects randomized to open-label liraglutide will begin the trial (Visit 3/Day 1) on 0.6 mg/day liraglutide.

At Visit 4/Day 7, the dose of liraglutide should be increased to 1.2 mg/day.

At Visit 5/Day 14, the dose of liraglutide should be increased to 1.8 mg/day.

The titration regimen for liraglutide may be modified to appropriately manage observed GI intolerance. The liraglutide dose should be titrated to the full target dose (1.8 mg/day) no later than Day 21. Subjects who cannot tolerate the 1.8 mg/day dose of liraglutide may continue in the trial on the 1.2 mg/day dose.

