8.2.4 Analysis Populations

8.2.4.1 Efficacy Analysis Populations

The Full Analysis Set (FAS) population will serve as the primary population for the analysis of efficacy data in this study. The FAS population includes subjects who take at least one dose of study therapy and have at least one efficacy measurement either at baseline or during the treatment period. Subjects will be included in the treatment group to which they were randomized.

A secondary population for analyzing primary and key secondary efficacy endpoints at Week 12 will be the Per-Protocol (PP) population. All randomized subjects who take at least one dose of study medication, with a measurement at baseline and the time point of interest (Week 12), without the protocol deviations described below will be included in this population.

Protocol deviations used to determine the PP population are not just a repetition of the exclusion and inclusion criteria in the protocol, but a clinical assessment of deviations from the protocol-specified criteria that will either affect or confound the measures of efficacy. The following rules define protocol violators during the trial period of interest (Day 1 through Week 12) and will be used to identify such subjects prior to unblinding. Subjects with any of the following violations will be excluded from the PP population at all time points.

- **Drug compliance:** A subject will be excluded from the PP population due to low compliance if either of the following applies:
 - Compliance assessed by prime therapy records provided by the investigator in the eCRF is <90%.
 - <75% of evaluable trough PK samples have quantifiable concentrations. This
 criterion is applicable only to subjects in the MK-8521 and liraglutide groups.
 

Protocol/Amendment No.: 004-02

Additionally, a site will be deemed to have low compliance and all subjects from that site (including those randomized to the placebo group) will be excluded from the PP population if either of the following applies:

- o For sites with exactly 2 subjects randomized to active groups, both of these subjects have low compliance based on trough PK criterion noted above.
- o For sites with 3 or more subjects randomized to active groups, ≥50% of subjects have low compliance based on the trough PK criterion noted above.
- Use of prohibited medications: The list of prohibited medications can be found in Section 5.5.

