 - o If a subject takes any prohibited antihyperglycemic medications after randomization (Visit 3/Day 1) for a total of ≥14 days or ≥7 consecutive days, he/she will be identified as a protocol violator.
 - o A subject with pharmacologic doses of corticosteroid use ≥ 2 consecutive weeks after randomization will be identified as a protocol violator.
- Incorrect double-blind study medications: If a subject receives incorrect double-blind study medication for a total of ≥14 days during the trial period of interest, then he/she will be identified as a protocol violator.
- Subjects who cannot tolerate 0.5 mL/day from Vial D: If a subject does not tolerate the full target dose of 0.5 mL/day MK-8521 from Vial D, he/she will be identified as a protocol violator. This criterion will only be applied to subjects randomized to the MK-8521 300 µg group.

The final determination on protocol deviations, and thereby the composition of the PP population, will be made prior to the final unblinding of the database and will be documented.

An additional secondary population to analyze the efficacy endpoints will be the modified FAS (mFAS). The modified FAS population is a subset of FAS population that excludes sites identified as having low compliance (as described in the drug compliance description for the PP population above).

The number of subjects included in the FAS, PP and mFAS populations may vary across endpoints due to the degree of missing data for each endpoint. Any substantial differences between conclusions based on the FAS, PP population, and mFAS population will be investigated.

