
Protocol/Amendment No.: 004-02

In the event that fewer than 75% of the subjects in the 300 μ g dose group receive the full target dose, suggestive of dose-intolerance, the hypothesis test MK-8521 180 μ g vs. placebo will be performed first. In this case if the 180 μ g dose vs. placebo is statistically significant, the primary hypothesis (for A1C) will be considered met and then the 300 μ g dose will be tested.

If success is achieved in the test of the primary hypothesis (i.e., at least one dose of MK-8521 provides significantly greater reduction in A1C relative to placebo following the testing procedure described above), then each of the MK-8521 doses will be compared to liraglutide using the same ordered testing procedure above. Continuous efficacy endpoints such as FPG, body weight, LDL-cholesterol level, HDL-cholesterol level, triglyceride level, systolic blood pressure (SBP), and diastolic blood pressure (DBP) will be analyzed using the above cLDA method described for A1C. Change and percent change from baseline in triglycerides will be analyzed using multiple imputation (MI) of missing values (if any) in conjunction with a robust regression (RREG) approach that uses M-estimation. Because the percent change in triglycerides typically has a skewed distribution, the cLDA model which is based on the symmetric normal distribution is not appropriate.

The primary (A1C) and key secondary endpoints (FPG and body weight) will also be analyzed in the PP population using an ANCOVA model. The ANCOVA model will include treatment, stratification factors of A1C (<8.5%, $\ge8.5\%$), BMI (<30 kg/m², ≥30 kg/m²) and AHA washout status (Yes, No), and baseline value. By definition, there will be no missing outcome data in the PP population.

Key efficacy endpoints will also be analyzed in the mFAS population using the same statistical methods stated for the FAS population.

Table 12 summarizes the analysis strategy for all efficacy endpoints. The strategy to address multiplicity issues with regard to multiple treatment comparisons and multiple endpoints is described in Section 8.2.6, Multiplicity.

Table 12 Analysis Strategy for Efficacy Endpoints

Endpoint (All at Week 12)	Approach	Statistical Method	Analysis Population	Missing Data Approach
Primary				
Change from baseline in A1C	P	cLDA	FAS	Model-based
Change from basefine in ATC	S	ANCOVA	PP	NA
	S	cLDA	mFAS	Model-based
Key Secondary				
Change from baseline in FPG	P	cLDA	FAS	Model-based
	S	ANCOVA	PP	NA

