8.2.5.2 Safety Analyses

The ASaT population and modified ASaT population will be employed for safety analyses. Safety and tolerability will be assessed following a tiered approach by clinical review of all relevant parameters including AEs, predefined limits of change (PDLC), laboratory tests, and vital signs. For all comparisons described below, each of the two doses of MK-8521 will be compared versus placebo and versus liraglutide.

The analysis of safety parameters will follow a tiered approach. The tiers differ with respect to the analyses that will be performed. Safety parameters or adverse events of interest that are identified *a priori* constitute "Tier 1" safety endpoints that will be subject to inferential testing for statistical significance with p-values and 95% CIs provided for between-group comparisons using the Miettinen and Nurminen method [23], an unconditional, asymptotic method. Other safety parameters will be considered Tier 2 or Tier 3. Tier 2 parameters will be assessed via point estimates with 95% CI provided for between-group comparisons; only point estimates by treatment group are provided for Tier 3 safety parameters.

Membership in Tier 2 requires that at least 4 subjects in any treatment group exhibit the event or meet PDLC criterion; all other AEs and PDLCs will belong to Tier 3.

The threshold of at least 4 events was chosen because the 95% CI for the between-group difference in percent incidence will always include zero when treatment groups of equal size

Protocol/Amendment No.: 004-02

each have less than 4 events and thus would add little to the interpretation of potentially meaningful differences. Because many 95% CIs may be provided without adjustment for multiplicity, the CIs should be regarded as a helpful measure to be used as a flagging method—to identify events of potential clinical relevance, that require additional review—and not a formal method for assessing the statistical significance of the between-group differences in AEs and PDLCs.

Table 13 summarizes the analysis strategy for safety endpoints. In addition, as some of the subjects in the MK-8521 300 μ g and liraglutide arms may not get to the full target dose, sensitivity analyses including only subjects with the full dose may be performed for Tier 1 safety parameters.

Table 13 Analysis Strategy for Safety Endpoints

Tier	Safety Endpoint	p-Value	95% CI for Treatment Comparisons	Descriptive Statistics
Tier 1	AE of symptomatic hypoglycemia	X	X	X

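### The per-protocol tolerance exclusion covers the MK-8521 300 µg arm but not liraglutide, so per-protocol comparisons of the two arms are selected on one side

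*Combined protocol and SAP*

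**What the plan says.** The PP set is a secondary efficacy population. Section 8.2.4.1: "A secondary population for analyzing primary and key secondary efficacy endpoints at Week 12 will be the Per-Protocol (PP) population". Violators are removed completely: "Subjects with any of the following violations will be excluded from the PP population at all time points". Section 8.2.5.1 states that A1C, FPG and body weight "will also be analyzed in the PP population using an ANCOVA model".

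One violation concerns tolerance of the target dose: "If a subject does not tolerate the full target dose of 0.5 mL/day MK-8521 from Vial D, he/she will be identified as a protocol violator". The next sentence restricts it: "This criterion will only be applied to subjects randomized to the MK-8521 300" µg group.

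Two step-downs are permitted. For the blinded arms, Section 2.1: "Subjects who cannot tolerate 0.5 mL/day from Vial D may continue in the trial on 0.3 mL/day" per vial. For liraglutide, Section 5.2.1.2: "Subjects who cannot tolerate the 1.8 mg/day dose of liraglutide may continue in the trial on the 1.2 mg/day dose".

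The safety section treats the two active arms together. On Tier 1 parameters, Section 8.2.5.2 names the 300 µg arm alongside the comparator: "liraglutide arms may not get to the full target dose, sensitivity analyses including only subjects with the full dose may be performed".

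**The concern.** Whether a subject tolerates the target dose is known only after randomization, and it may be related to the Week 12 outcome. If it is used to exclude subjects from one arm only, the two groups are no longer defined in the same way. Here the 300 µg PP group becomes those who tolerated 300 µg, while the liraglutide PP group remains everyone who otherwise complied, whether on 1.8 mg or 1.2 mg. Staying on 1.2 mg is a real reduction in active drug, just as moving from 300 µg to 180 µg is.

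Section 8.2.4.1 says that substantial differences between FAS, PP and mFAS conclusions will be investigated, and Section 8.2.9.2 adds PP analyses at the interim. A PP result for 300 µg against liraglutide that departs from the FAS result could come from the exclusion rule rather than from adherence, and a reader of the PP table could not tell which.

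**Working it through.** **Which PP rules reach a subject who steps down?** Section 8.2.4.1 lists four kinds of violation.

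- Drug compliance: the recorded-compliance criterion counts days with the prescribed injections taken (Section 8.2.10), and the PK criterion counts quantifiable trough samples. Neither refers to dose level.
- Prohibited medication: not relevant to a step-down.
- Incorrect double-blind medication: not relevant to open-label liraglutide or to a permitted step-down.
- Not tolerating 0.5 mL from Vial D: 300 µg arm only.

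| Arm | After step-down | Active dose changed? | Removed from PP for it? |
|---|---|---|---|
| 300 µg | 0.3 mL from each vial (180 µg) | yes | yes |
| Liraglutide | 1.2 mg | yes | no |
| 180 µg | 0.3 mL from each vial (180 µg) | no | no |
| Placebo | 0.3 mL from each vial | no (none given) | no |

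Of the two arms in which a step-down changes the active dose, the rule treats one and omits the other.

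**Design inputs, reproduced first** (Section 8.2.7: 40 per arm, attrition 0.08 and 0.16, correlation 0.76732, conditional SD 1.1% for A1C and 2.7 kg for weight).

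- Effective n = 1 / [0.76732²/(40 × 0.92) + (1 − 0.76732²)/(40 × 0.84)] = 35.4, against a stated 35.
- Power at n = 35: A1C (0.8%) 86.0%, stated about 85%; weight (2 kg) 87.3%, stated about 87%.

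The plan gives no figure for the effect of the PP rule, so the next step is illustrative.

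**Illustration.** Let f be the fraction of the 300 µg arm removed and g the mean Week 12 difference between its tolerators and non-tolerators. The 300 µg mean is (tolerator mean − f × g) before exclusion and the tolerator mean after it, so the contrast moves by f × g. Neither f nor g is in the documents. I take f = 10% to 25%, g = 0.2% to 0.8% for A1C and 0.5 to 2 kg for weight. Completers per arm = 40 × 0.84 = 33.6, and SE = SD × √[1/(33.6(1 − f)) + 1/33.6].

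| Endpoint | f | g | Shift f × g | SE | Nominal 5% test, unselected arms equal |
|---|---|---|---|---|---|
| A1C | 10% | 0.2% | 0.02% | 0.276 | 5.1% |
| A1C | 25% | 0.4% | 0.10% | 0.290 | 6.4% |
| A1C | 25% | 0.8% | 0.20% | 0.290 | 10.6% |
| Weight | 10% | 0.5 kg | 0.05 kg | 0.677 | 5.1% |
| Weight | 25% | 1 kg | 0.25 kg | 0.712 | 6.4% |
| Weight | 25% | 2 kg | 0.50 kg | 0.712 | 10.8% |

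Against the stated A1C half-width of 0.52%, the A1C shifts are 0.02/0.52 = 4% to 0.20/0.52 = 38%. If g = 0 there is no shift, and if g is negative the shift reverses. The same rule in both arms changes the shift to f₃₀₀g₃₀₀ − f_L g_L, which is zero only if those products match.

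**The case against.** The restriction has a reason. In the 300 µg arm a Vial D step-down leaves the subject on 180 µg, another randomized arm's dose. In the placebo and 180 µg arms it changes no active drug. Section 8.2.4.1 says PP deviations are those that affect or confound efficacy, and the Summary of Changes shows the limit was deliberate. This stands for placebo and 180 µg. It does not cover liraglutide, where the step-down does lower the active dose.

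A reader might infer that placebo step-downs should leave the PP set too. The documents do not support that. Placebo is in the same position as the 180 µg arm, and removing step-downs from placebo but not from 180 µg would make the 180 µg versus placebo PP contrast, now symmetric, one-sided. Removing those who do not tolerate placebo volume would also not give a group comparable to those who tolerate 300 µg of active drug. The one-sidedness of 300 µg against placebo remains, but it needs a different answer.

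The consequences are also limited. FAS by randomized group is primary and carries the ordered tests. The mFAS analysis is a second check without a tolerance exclusion. Section 8.2.6 classes liraglutide comparisons as supportive or exploratory, and the PP paragraph of Section 8.2.5.1 names no liraglutide contrast, although estimation against liraglutide is a secondary objective in Section 3.2. At the interim, FAS is the stated population and futility is non-binding and must be met for both doses. All of this stands and limits the point to the reading of a secondary analysis.

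**Conclusion.** The inconsistency is confirmed from the text: not tolerating the target dose is a PP violation in the 300 µg arm and not in the liraglutide arm, and the plan's own safety section recognises the problem in both. Any PP comparison of these arms, including one made at the interim, is not like for like.

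Its size is unknown. The 0.02 to 0.20 A1C points and 0.05 to 0.50 kg above rest entirely on assumed f and g. A reader might infer from the 75% rule in Sections 8.2.5.1 and 8.2.6 that the sponsor expects a quarter of the 300 µg arm, 10 of 40, to miss target. That rule is a contingency, neither a forecast nor a cap. A reader might also infer that the shift must favour MK-8521. That does not follow: intolerant subjects could lose more weight, and Section 4.2.2 reports near-maximal glycemic effects from 120 µg MK-8521 and 1.2 mg liraglutide upward, which points to a small A1C gap from dose alone. Nor does the point reach the primary result: the FAS analysis and the formal hypothesis tests are unaffected.

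**What to change.** Extend the tolerance bullet in Section 8.2.4.1 so that not tolerating the arm's own full target dose is a PP violation in the liraglutide arm (1.8 mg) as well as in the 300 µg arm. Leave placebo and 180 µg as written, and say why: the Vial D step-down does not change their active dose.

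Because the exclusion stays one-sided against placebo, also report the PP ANCOVA for 300 µg versus placebo without the tolerance exclusion, for A1C, FPG and body weight. Apply both changes to the interim PP analyses. State with the PP results that excluding on tolerance in both active arms aligns their definitions but does not restore randomization.

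The cost is one bullet and one sensitivity analysis. Some liraglutide subjects leave the PP set: under the assumed 10% to 25%, 0.10 × 33.6 = 3.4 to 0.25 × 33.6 = 8.4. The A1C standard error for 300 µg versus liraglutide then rises from 0.276 to 1.1 × √(2/30.24) = 0.283, or from 0.290 to 1.1 × √(2/25.2) = 0.310. Information on who reached full dose is already needed in both arms for the full-dose safety analysis in Section 8.2.5.2. No dosing rule changes.

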8.2.4.2 Safety Analysis Populations

The all subjects as treated (ASaT) population will be the primary population for the analysis of safety data in this study. The ASaT population consists of all randomized subjects who received at least one dose of study treatment. Subjects will be included in the treatment group corresponding to the study treatment they actually received for the analysis of safety data using the ASaT population. For most subjects this will be the treatment group to which they were randomized. Subjects who took incorrect study treatment for the entire treatment

Protocol/Amendment No.: 004-02

period will be included in the treatment group corresponding to the study treatment they actually received.

Supplementary safety analyses will be performed in the modified ASaT population, which is the subset of the ASaT population that excludes sites identified as having low compliance (as described in the drug compliance description for the PP population in Section 8.2.4).

8.2.5 Statistical Methods

Statistical testing and inference methods for efficacy and safety analyses are described in Section 8.2.5.1 and Section 8.2.5.2, respectively. Efficacy results that will be considered to be statistically significant after consideration of the strategy for controlling the Type I error are described in Section 8.2.6 - Multiplicity. Nominal p-values may be computed for other efficacy analyses as a measure of strength of association between the endpoint and the treatment effect rather than formal tests of hypotheses. All statistical tests will be conducted at the 2-sided 0.05 significance level.

8.2.5.1 Efficacy Analyses

To address the primary objective, the analysis of change from baseline in A1C at Week 12 will be performed using a constrained longitudinal data analysis (cLDA) method proposed by Liang and Zeger. This repeated measures model assumes a common mean across treatment groups at baseline and a different mean for each treatment at each of the post-baseline time points. The response vector consists of baseline and the values observed at each postbaseline time point. The cLDA model will include terms for treatment, time, stratification factors of A1C (<8.5%, $\ge8.5\%$), BMI ($<30 \text{ kg/m}^2$, $\ge30 \text{ kg/m}^2$) and AHA washout status (Yes, No), and the interaction of time by treatment. Time is treated as a categorical variable so that no restriction is imposed on the trajectory of the mean over time. An unstructured covariance matrix will be used to model the correlation among repeated measurements and hence avoids the potential bias that could result from the use of specific structured covariance models. If the unstructured covariance model fails to converge with the default Newton-Raphson algorithm, the Fisher scoring algorithm or other appropriate methods can be used to provide initial values of the covariance parameters. In the rare event that none of the above methods yield convergence, a structured covariance such as Toeplitz can be used to model the correlation among repeated measurements. In this case, the empirical option will be used because the sandwich variance estimator is asymptotically unbiased while the model-based variance estimator can substantially overestimate or underestimate the true variance. The Kenward-Roger adjustment will be used with restricted (or residual) maximum likelihood (REML) to make proper statistical inference. The cLDA model uses the maximum likelihood principle to estimate the parameters and account for missing data in an implicit fashion.

The primary hypothesis will be assessed by an ordered testing procedure, comparing each of the two MK-8521 doses to placebo at Week 12, using the above cLDA model. This testing procedure first tests the 300 μg dose. If a statistically significant result (i.e., p<0.05) is observed on the 300 μg dose, the primary hypothesis (for A1C) is considered met and then the 180 μg dose is tested. The secondary hypotheses (for body weight and FPG) will be assessed only if the primary hypothesis is met, regardless of the outcome of the 180 μg vs placebo comparison.

Protocol/Amendment No.: 004-02

In the event that fewer than 75% of the subjects in the 300 μ g dose group receive the full target dose, suggestive of dose-intolerance, the hypothesis test MK-8521 180 μ g vs. placebo will be performed first. In this case if the 180 μ g dose vs. placebo is statistically significant, the primary hypothesis (for A1C) will be considered met and then the 300 μ g dose will be tested.

If success is achieved in the test of the primary hypothesis (i.e., at least one dose of MK-8521 provides significantly greater reduction in A1C relative to placebo following the testing procedure described above), then each of the MK-8521 doses will be compared to liraglutide using the same ordered testing procedure above. Continuous efficacy endpoints such as FPG, body weight, LDL-cholesterol level, HDL-cholesterol level, triglyceride level, systolic blood pressure (SBP), and diastolic blood pressure (DBP) will be analyzed using the above cLDA method described for A1C. Change and percent change from baseline in triglycerides will be analyzed using multiple imputation (MI) of missing values (if any) in conjunction with a robust regression (RREG) approach that uses M-estimation. Because the percent change in triglycerides typically has a skewed distribution, the cLDA model which is based on the symmetric normal distribution is not appropriate.

The primary (A1C) and key secondary endpoints (FPG and body weight) will also be analyzed in the PP population using an ANCOVA model. The ANCOVA model will include treatment, stratification factors of A1C (<8.5%, $\ge8.5\%$), BMI (<30 kg/m², ≥30 kg/m²) and AHA washout status (Yes, No), and baseline value. By definition, there will be no missing outcome data in the PP population.

Key efficacy endpoints will also be analyzed in the mFAS population using the same statistical methods stated for the FAS population.

Table 12 summarizes the analysis strategy for all efficacy endpoints. The strategy to address multiplicity issues with regard to multiple treatment comparisons and multiple endpoints is described in Section 8.2.6, Multiplicity.

Table 12 Analysis Strategy for Efficacy Endpoints

Endpoint (All at Week 12)	Approach	Statistical Method	Analysis Population	Missing Data Approach
Primary				
Change from baseline in A1C	P	cLDA	FAS	Model-based
Change from basefine in ATC	S	ANCOVA	PP	NA
	S	cLDA	mFAS	Model-based
Key Secondary				
Change from baseline in FPG	P	cLDA	FAS	Model-based
	S	ANCOVA	PP	NA
	S	cLDA	mFAS	Model-based
Change from baseline in body weight	P	cLDA	FAS	Model-based
	S	ANCOVA	PP	NA
	S	cLDA	mFAS	Model-based
Other Endpoints				
Change and percent change from baseline in LDL and				
HDL	P	cLDA	FAS	Model-based
Change from baseline in SBP and DBP				
Change and percent change from baseline in	P	Robust	FAS	Multiple
triglycerides	Р	Regression	FAS	Imputation
P=Primary; S=Secondary				

Protocol/Amendment No.: 004-02

The following exploratory efficacy analyses may be performed. Analysis methods will be described in a separate document, as appropriate.

- Insulin secretion (HOMA-β) and insulin resistance (HOMA-IR). A decision for the analysis will be based on potential for utility in light of emerging clinical efficacy and safety outcomes.
- Glucagon receptor activation biomarkers (including ketones, glucagon, FGF-21 and kisspeptin). Analyses may be performed if the primary hypothesis is met or if the results are considered important for future dual peptide programs.
- If fewer than 75% of the subjects in the 300 μg dose group receive the full target dose, an additional analysis with pooling of subjects on 180 μg dose may be performed. Those subjects not tolerating the 300 μg dose and continuing on the 180 μg dose will be pooled with the subjects in the 180 μg dose group.
- The relationship between genetic variation and response to the treatments administered, and variation across the human genome with clinical data collected in this study may be analyzed. A decision for the analysis will be based on potential for utility in light of emerging clinical efficacy and safety outcomes.

Due to the limited duration of analyte stability in collected PK samples, it is necessary to conduct PK sample analysis on a rolling basis while the study is ongoing. Early unblinding limited to staff critical for the conduct of PK sample analyses will occur to allow PK analysis of subjects who received the drug (MK-8521) being measured. No multiplicity adjustment is being made since the conduct of the study is not dependent on the unblinding for early PK analysis. Unblinded PK data or results will not be shared with the protocol team prior to study completion and database lock.

